### Study Population and Sample Size

Eligible Veterans are age  $\geq 50$  with polypharmacy as defined by  $\geq 5$  medications based on the pre-hospital admission; ability to provide consent (or proxy); speaks English; does not reside in long-term care or receive hospice services; have a recommendation or referral to a skilled nursing facility (SNF). All eligible Veterans will be approached for consent with an original enrollment goal of 540.

The population and sample size were adjusted mid-study due to the significant enrollment and retention challenges caused by the COVID-19 pandemic. It was determined that a sample of 260 Veterans was sufficient to provide power greater than 93% for both the primary and secondary outcomes. Additionally, Veterans who were recommended SNF placement but ultimately discharged from hospital to home were approved to remain in study, which improved the study retention rate.

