## STUDY PROCEDURES

Data collection includes Veteran descriptive data along with geriatric syndromes, medications, health status, safety, and implementation science as noted in the table below. Upon enrollment, the Veteran will complete interviewer-administered questionnaires (marked with an asterisk below) with interviews conducted by trained study personnel. In the event the Veteran is unable to complete assessments (e.g., delirious, cognitively impaired), their designated surrogate will be asked to complete the assessments for which surrogate responses have been validated. Assessments that can be completed by surrogates are the ICIQ (urinary incontinence), DETERMINE, falls, pressure ulcers, medication history, and demographics. The remainder of the data will be abstracted from each patient's medical record; however, total number and type of medications will be determined based on a

combination of patient interview, medical record and pharmacy refill history to ensure an accurate, complete medication list.

The data shown in the below table for the “SNF” column is abstracted from SNF medical records; thus, research personnel will not interview the participant again during their SNF stay. However, participants will be contacted via telephone by research personnel at 7 and 90 days after they leave the SNF. If the Veteran is willing to also complete our implementation evaluation interview to assess barriers and enablers of deprescribing during their routine 7-day follow-up call, we will conduct this additional interview at the current 7-day follow-up timepoint in conjunction with other 7-day assessments. However, in consideration of Veteran response burden, we will provide the Veteran with the option to schedule the implementation evaluation interview component anytime during the initial 14-days following SNF discharge, based on the preference and convenience of the Veteran, so that they may choose to complete this interview separately. Both the intervention and control group will be monitored using that same data collection schedule and measures.

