## Primary Outcomes – Medications

Total number of medications: Data collection begins with the Veteran's Essential Medication Review List (EMLR). After this list is abstracted from the medical record, a study NP or PharmD pulled the Controlled Substance Monitoring Database report, called non-VA pharmacies for recently filled prescriptions, reviewed non-VA medical records (i.e., outside hospital or SNF records), and interviewed the Veteran or their surrogate. We included all medications, either prescription or over-the-counter (OTC) that were administered by the following routes: oral, intravenous, intramuscular, sublingual, or ophthalmologic. Veterans (or their surrogate) were given specific prompts if they reported no OTC usage, for example, asking them if they take anything for constipation or allergies. If a patient was admitted from an institutional setting (e.g., outside hospital, SNF, ALF), we request a copy of the medication administration record from the previous 30 days. Medications are considered current/active if the Veteran took it within 30 days of hospitalization. The hospital discharge and SNF discharge medication lists, serve as the outcome data for those respective time points. During the follow-up calls, the study NP or PharmD systematically asked the Veteran for the status of each medication on the enrollment list and discharge lists to determine if and how they are taking it. Afterwards the study clinician prompted the Veteran for any new medications they may be taking.

Potentially Inappropriate Medications (PIMs): We used previously published and validated lists including the Beers criteria, the STOPP criteria, and the RASP list, which have a large degree of overlap. The total number of PIMs is the sum of medications that are found on these lists.

Drug Burden Index (DBI): This score is calculated separately for anticholinergic and sedative medications, which have been linked to functional impairment, falls, and delirium. The DBI is the sum of each individual anticholinergic/sedative medication's prescribed daily dose divided by the sum of the minimum effective dose (per the FDA minimum recommended dose) and the patient's daily dose. The DBI is calculated for all medications including OTCs. We will calculate the DBI at each timepoint, and this will capture dose reductions even when the total number of medications is not reduced.

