## **Post-Intervention Follow-Up**

The intervention ends at hospital discharge. Originally, if the Veteran discharged to any location other than SNF, they were discontinued from study. Due to retention concerns, the IRB approved the retention of Veterans who discharged home (beginning in March 2021).

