### **7- and 90-Day Follow-Up**

The 7-Day follow-up call occurs 7 days after SNF discharge ( $\pm 3$  days), and the 90-Day call occurs 90 days after SNF discharge ( $\pm 10$  days). The study NP or PharmD asks the Veteran to have their medication bottles, pill organizer, and list nearby during the call. If a surrogate assists with medication management, we also ask that person to be available. The Veteran lists of the medications they are currently taking with the dose and frequency information. Afterwards, the study clinician will inquire about medications from enrollment or discharge lists that the Veteran did not address in order to confirm their usage or discontinuation. After the medication history is obtained, the study team administers the geriatric syndrome and medication adherence assessments.

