### Outcomes

**Hypotheses 1a -1b:** Among participants assigned to the intervention group, we will summarize both the number of deprescribing *recommendations* and the number of actual medication *changes* at hospital and SNF discharge and 90-days following SNF discharge. The effect of the intervention on the total number of medications, PIMs, and medications associated with geriatric syndromes at hospital discharge, SNF discharge, and 90-days following SNF discharge will be assessed using mixed effects Poisson regression, allowing for overdispersion (more or less variability than is expected under the Poisson regression model), and adjusting for measurement time point (as a categorical covariate) and the total number of medications at enrollment and the interaction of intervention and time point. The heterogeneity in outcome measures across participants will be modeled using a random intercept term, indexed by subject. Heterogeneity among VA providers and SNFs in the effectiveness of intervention will be modeled using a random intervention effect, indexed by VA provider and SNF. The overall intervention effect will be evaluated using a Wald-type multiple degree-of-freedom test against the null hypothesis of no effect at any time point. The intervention effect at each time point will be summarized using a Wald-type 95% confidence interval. Model fit will be assessed by examining the associated Pearson residuals and other graphical methods. Alternative regression techniques may be used in the case of poor fit, for example, negative-binomial regression. A secondary analysis to explore the possibility of intervention effect modification by hospital length of stay (e.g., longer stay may result in more deprescribing) will be implemented by considering the interaction of hospital length of stay with intervention.

**Hypothesis 1c:** The effect of intervention on the anticholinergic and sedative drug burden index scores at hospital discharge, SNF discharge, and 90-days following SNF discharge will be assessed using linear mixed effects

regression, adjusting for measurement time point, its interaction with intervention and using random effects, testing and summary methods as described for Hypotheses 1a, 1b and 1d. Model fit will be assessed using residual diagnostics and graphical methods. Due to the constrained nature of the DBI values, a ‘beta’ regression method may be required, which is suitable for scores that often occur at a boundary.

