### **Protection Against Risks**

The deprescribing intervention protocol is a carefully developed, multi-stage process that includes the independent review of multiple clinicians, each of whom can stop any recommended deprescribing action. This includes the research team pharmacist or nurse practitioner, primary hospital team, and the Veteran or their surrogate. Each medication recommended for deprescribing will be considered for its potential for physiologic withdrawal, pharmacokinetic/pharmacodynamic effects, and medical condition exacerbation. Strategies to protect against risks are as follows:

- Any medication believed to have increased potential for physiologic withdrawal will undergo a prescribed drug taper, where the identified drug will not be reduced by more than 25% to 50% during any 1-week interval when a patient is receiving greater than the minimum therapeutic dose.

- Deprescribing pharmacists / NPs will alert the primary medical team and make recommendations to the post-acute care for surveillance of symptoms, signs (e.g., vital signs), labs (e.g., electrolytes, INR), or follow-up tests (e.g., EKG).
- A strength of this trial is that we will be able to monitor for exacerbations of medical conditions in a post-acute care setting (mean length of stay = 26.9 days), where monitoring of vital signs and symptoms are done daily by licensed nurses. In addition, during the “SNF handover” process, all discontinued medications will be clearly delineated along with any expected signs or symptoms that may be expected to return.
- Medications can be restarted or increased at any time should adverse pharmacokinetic/pharmacodynamics effects or a physiologic drug withdrawal effect be detected.

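### Veterans discharged home are kept in the study from March 2021, but their 7- and 90-day calls have no stated time zero and the analysis set leaves them out

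*Combined protocol and SAP*

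**What the plan says.** **Retention.** The Précis (Study Population and Sample Size) says that "Veterans who were recommended SNF placement but ultimately discharged from hospital to home were approved to remain in study". Post-Intervention Follow-Up gives the date: "Due to retention concerns, the IRB approved the retention of Veterans who discharged home (beginning in March 2021". Before that, a Veteran discharged anywhere other than a SNF was discontinued.

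**Timing of outcomes.** Study Procedures says that "participants will be contacted via telephone by research personnel at 7 and 90 days after they leave the SNF". The section 7- and 90-Day Follow-Up repeats it: "The 7-Day follow-up call occurs 7 days after SNF discharge" (window 3 days either side), and "the 90-Day call occurs 90 days after SNF discharge" (window 10 days either side). The Schedule of Assessments has a SNF-discharge column and two post-SNF columns. For medications, "The hospital discharge and SNF discharge medication lists, serve as the outcome data for those respective time points".

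**Analysis.** Under Statistical Considerations, Outcomes, the medication counts are modelled at hospital discharge, SNF discharge and 90 days after SNF discharge, with a random intervention effect indexed by VA provider and SNF. The test is joint: "The overall intervention effect will be evaluated using a Wald-type multiple degree-of-freedom test against the null hypothesis of no effect at any time point". The drug burden index uses the same time points and testing. The Aim 2 outcomes are read at 7 and 90 days after SNF discharge.

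**Analysis set.** The section on Randomization, Intent-to-Treat, & Safety Outcomes admits randomised Veterans whose hospital discharge was to a SNF, and not those who went home or to hospice. It then promises both intent-to-treat and per-protocol analyses.

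**The concern.** The retention rule was changed, but the definitions that depend on it were not. Two things follow.

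First, a Veteran who goes straight home never leaves a SNF, so the text gives no date from which to count 7 or 90 days. Retention then yields no defined post-hospital outcome.

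Second, the analysis set depends on discharge destination. Destination is known only after randomisation and after the in-hospital intervention, so the groups compared are no longer the groups randomised. The exclusion also discards the hospital-discharge medication list, which every Veteran discharged home has and which is the outcome closest to the intervention. An analysis restricted in this way is not intent-to-treat, although the same section uses that name.

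**Working it through.** This is a matter of definitions, so the passages are compared first and the arithmetic only gives scale.

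**1. What exists for a home-discharged Veteran at each time point**

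| Time point | Does the outcome exist? | Is its timing defined? | In the primary medication model? |
|---|---|---|---|
| Hospital discharge | Yes (hospital discharge list) | Yes | Yes |
| SNF discharge | No | No | Yes |
| 7 days | Obtainable by telephone | No time zero or window | No |
| 90 days | Obtainable by telephone | No time zero or window | Yes |

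Two of the three points in the primary medication model are affected (SNF discharge and 90 days). For the Aim 2 outcomes, both follow-up points (7 and 90 days) are affected. Only the SNF-discharge value truly does not exist. No section supplies a substitute time zero, and no level of the SNF-indexed random effect is defined for a Veteran who entered no SNF.

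**2. Analysis set.** The analysis-set sentence removes home-discharged Veterans from all rows of the table, including the first. This cannot be squared with the retention rule or with intent-to-treat.

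**3. How much of enrolment the retention rule covers**
- Enrolment, October 2019 to November 2022 (Study Design), counted inclusively: 3 + 12 + 12 + 11 = 38 months.
- Rule in force, March 2021 to November 2022: 10 + 11 = 21 months.
- 21 / 38 = 55% of calendar enrolment. This is a share of time, not of participants.

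**4. Elapsed time if hospital discharge were time zero for home-discharged Veterans**
- Input: "mean length of stay = 26.9 days" in SNF (Protection Against Risks).
- 7-day call: day 7 for home, against 26.9 + 7 = 33.9 for SNF.
- 90-day call: day 90 for home, against 26.9 + 90 = 116.9, about 117, for SNF.
- With the 10-day window, these are days 80 to 100 against 106.9 to 126.9 at the mean stay. The windows do not overlap there, although individual stays will vary around the mean.

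**5. What cannot be computed.** The plan's figure of more than 93% power with 260 Veterans cannot be reproduced, because no effect size, variability, significance level or attrition is given for it. The number discharged home is not given either. Any loss of power or precision would therefore rest wholly on assumed inputs, and none is claimed.

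**The case against.** The strongest reply is that this is a drafting gap. The calls are telephone interviews using bottles, pill organiser and list, and do not depend on where the Veteran was discharged. Hospital discharge date and disposition are abstracted for everyone (Description of Assessments, Demographic and Administrative Data). That stands for the 7- and 90-day outcomes: a reader might infer that they cannot be scored at all, but they lack only a stated origin and window. It does not answer the analysis-set sentence, which is an explicit rule. That sentence may be left over from the time when home discharges were discontinued, but the documents do not say so.

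Four stronger readings are tempting and are not supported.

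- *Retention shrinks the SNF-discharge sample and widens its standard error.* Under the former rule these Veterans were discontinued and had no SNF-discharge value either. For a given number randomised, retaining them removes nobody from that time point.
- *The model invents SNF-discharge counts for people who never entered a SNF.* A mixed model is fitted to the records that exist, and an absent record leaves the fit unchanged whatever it is called. The distinction matters for multiple imputation, which the Missing Data section plans only as a sensitivity analysis if missingness is unbalanced between arms.
- *Mixing 90 and 117 days biases the arm comparison.* Time since hospital discharge already varies among SNF Veterans. Mixing durations changes what the 90-day contrast means. It would bias the comparison only if destination or length of stay differed by arm, and nothing in the documents shows that.
- *SNF discharge should leave the joint test.* Hypotheses 1a to 1d each name that time point, so removing it would change the stated primary test. That is a trade-off, not a correction.

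**Conclusion.** The point holds as an internal contradiction with a definite consequence. The plan retains home-discharged Veterans, gives their later calls no time zero, and admits to its analyses only Veterans discharged to a SNF. Followed literally, retention adds nothing to the analyses, an available hospital-discharge outcome is discarded, and the comparison is conditioned on a post-randomisation event under the name of intent-to-treat.

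Its reach is 55% of the enrolment calendar, two of three points in the primary medication model, and both follow-up points for Aim 2. The gap in time since hospital discharge, 26.9 days, assumes that the quoted mean SNF stay applies to this trial's participants. The number of Veterans affected is unknown, so the point does not rest on any estimate of lost power. Whether the arm comparison is actually biased cannot be told from the documents. The contradiction should be resolved before the analysis.

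**What to change.** 1. **Time zero.** In the Schedule of Assessments and in 7- and 90-Day Follow-Up, time the calls for home-discharged Veterans from hospital discharge, with the same windows (3 and 10 days either side).
2. **Analysis set.** Amend Randomization, Intent-to-Treat, & Safety Outcomes so that the intent-to-treat set is all randomised Veterans regardless of destination, with hospital-discharge data used for all. State how Veterans discontinued under the rule before March 2021 are handled.
3. **SNF-discharge contrast.** Keep it in the model and in the joint test, but label it as conditional on SNF admission. Under Missing Data, state that it is not imputed for home-discharged Veterans. Define their level in the SNF-indexed random effect.
4. **Reporting.** Report discharge destination by arm, and add a sensitivity analysis of the 90-day contrast by destination or by time since hospital discharge.

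The cost is a few sentences of protocol and analysis wording, one descriptive table and one sensitivity analysis. No new measurement is needed. The downside is that the 90-day point then combines two elapsed times, about 90 and 117 days. The sensitivity analysis shows whether that matters.

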### **Skilled Nursing Facility (SNF)**

The study team will contact the SNF weekly to monitor the Veteran's expected discharge date and monitor for any unplanned healthcare utilization. At the point of SNF discharge, the study team will request the Veteran's discharge medication list.

### **7- and 90-Day Follow-Up**

The 7-Day follow-up call occurs 7 days after SNF discharge ( $\pm 3$  days), and the 90-Day call occurs 90 days after SNF discharge ( $\pm 10$  days). The study NP or PharmD asks the Veteran to have their medication bottles, pill organizer, and list nearby during the call. If a surrogate assists with medication management, we also ask that person to be available. The Veteran lists of the medications they are currently taking with the dose and frequency information. Afterwards, the study clinician will inquire about medications from enrollment or discharge lists that the Veteran did not address in order to confirm their usage or discontinuation. After the medication history is obtained, the study team administers the geriatric syndrome and medication adherence assessments.

## **SAFETY MONITORING AND ASSESSMENTS**

We have established a system to report and track adverse events (AEs) including adverse drug withdrawal events (ADWEs), serious adverse events (SAEs), and Suspected Unexpected Serious Adverse Reaction (SUSARs). In this study, an AE is defined as any unplanned healthcare utilization or unexpected death (i.e., patient not receiving hospice services at time of death). These AEs are considered SAEs if they include any untoward medical outcome that results in the following: inpatient hospitalization or prolongation of existing hospitalization, life threatening condition with immediate risk of loss of life (including escalation of hospital care to Intensive Care Unit), or unexpected death. A SUSAR is an SAE that is suspected to be secondary to the drug withdrawal and is unexpected. Study personnel will monitor the safety of subjects and follow them until the event resolves or is explained.

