## Schedule of Assessments

Measures and Data Collection Timeline	Baseline Hospital	SNF Discharge	Post SNF Discharge	
			7-Days	90- Days
Descriptives			Telephone Interviews	
Demographics and Length of Stay	X	X		
Elixhauser Comorbidity Index	X			
Patient Attitudes Toward Deprescribing (PATD)*	X			X
Primary Outcome – Medications				
Total number and type of Routine and PRN Medications, including PIMs	X	X	X	X
Pharmacy Calls to Verify Refill History	X			X
Drug Burden Index (DBI)	X	X		X
Medication Adherence (ARMS)*	X		X	X
Secondary Outcome – Geriatric Syndromes				
Cognitive Impairment (BIMS)*	X		X	X
Delirium (BCAM)*	X		N/A	N/A
Depression (PHQ-9)*	X		X	X
Urinary Incontinence (ICIQ-UI SF)*	X		X	X
Unintentional Weight Loss (DETERMINE)*	X		X	X
Pain (Brief Pain Inventory, BPI-short form)*	X		X	X
Falls	X		X	X
Pressure Ulcers	X		X	X
Secondary Outcome – Health Status				
Functional Health Status (VES-13)*	X		X	X
Secondary Outcomes – Safety				
Unplanned Healthcare Utilization (hospitalizations, emergency room visits)		X	X	X
Adverse Drug / Withdrawal Events	X	X	X	X
Status: Long-Term Care, Hospice, Death		X	X	X
Implementation Evaluation				

Veteran & Provider Barriers and Facilitators	X		X	X
System-Level Factors related to Sustainability		X	X	X
Staff Time for Intervention Implementation	X	X	X	X
Stakeholder Input	X			

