### **Safety Outcomes**

**Unplanned Healthcare Utilization:** The study team will monitor Veterans’ healthcare utilization, both at the VA and outside the VA system, after study enrollment. During the consent process, Veterans sign a release of information form that allows the team to request records from non-VA entities. We will track all emergency room visits, hospitalizations, and deaths, and these events will be adjudicated by a blinded clinician (see Safety Assessments section).

**Adverse Drug Withdrawal Events (ADWEs):** any unplanned healthcare utilization is reviewed by a blinded physician co-investigator to determine if the event was medication related, and more specifically if it was related to medication withdrawal. The standardized adjudication form includes validated scales such as the Naranjo.

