### **Methods and Timing for Assessing, Recording, and Analyzing Safety Parameters**

#### **Notification of Unplanned Healthcare Utilizations and Deaths**

Unplanned healthcare utilization (intensive care unit transfers, emergency department visits and/or hospitalizations) and deaths are monitored throughout all study phases for each Veteran. The study coordinator and research assistant share a study patient panel in the electronic health record. Any time a participant is admitted to the Nashville VA Medical Center, they are alerted. To identify if a Veteran experience an unplanned healthcare utilization at an outside hospital (OSH), the Veterans are asked at each follow-up time point if they have been to an emergency room or had an inpatient stay, and if so, at what facility. Additionally, the research assistant or study clinician reviews VISTA for any uploaded OSH records at the time of the follow-up calls. The research assistant is responsible for requesting medical records from OSHs (and SNFs) relevant to the utilization.

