### **Review of Unplanned Healthcare Utilizations and Deaths**

Any unplanned healthcare utilization or unexpected death (e.g., patient not receiving hospice care) is reviewed to determine if it was an adverse event that was serious, related to the study, and unexpected (SUSAR). Once all necessary records have been obtained by the research assistant, the case is assigned to a physician co-investigator (adjudicator) blinded to group assignment. Through a structured review protocol of all relevant medical records from both within and outside of VA, the adjudicator uses an established methodology to determine the presence of serious medication errors. Clinician-adjudicators will decide whether the unplanned healthcare utilization is related to medication withdrawal (i.e., ADWE) using the 10-question Drug Withdrawal Probability Scale, a scale based on the Naranjo algorithm, which is a validated scoring system to assess causality of adverse drug events. ADWE will be coded as definite (>8), probable (5-8), possible (1-4), and doubtful (<1). For all ADWEs, clinician-adjudicators will then determine whether it was avoidable by any change in management.

After review by the clinician-adjudicator, the case is sent to the Principal Investigator to review to determine if the event was unexpected and/or study related. Should the event be determined as SUSAR (serious, unexpected, and study related) it will be reported as such to the DSMB and IRB as outlined below.

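### Withdrawal events count as safety events only if they lead to hospital-level care or death, so those managed on site by restarting a drug are not classified or reported as harms

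*Combined protocol and SAP*

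**What the plan says.** All references are to the combined protocol and SAP.

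- **Safety Monitoring and Assessments.** The tracking system covers "adverse events (AEs) including adverse drug withdrawal events (ADWEs", among other classes. The definition follows: "In this study, an AE is defined as any unplanned healthcare utilization or unexpected death".
- **Notification of Unplanned Healthcare Utilizations and Deaths.** The scope of utilization is given here: "Unplanned healthcare utilization (intensive care unit transfers, emergency department visits and/or hospitalizations) and deaths are monitored throughout all study phases".
- **Safety Outcomes.** In the ADWE entry, "any unplanned healthcare utilization is reviewed by a blinded physician co-investigator to determine if the event was medication related", and then whether it was due to withdrawal.
- **Review of Unplanned Healthcare Utilizations and Deaths.** The object judged is the utilization: "Clinician-adjudicators will decide whether the unplanned healthcare utilization is related to medication withdrawal (i.e., ADWE". Unexpected deaths also go to review.
- **Skilled Nursing Facility (SNF).** The team will "contact the SNF weekly to monitor the Veteran's expected discharge date and monitor for any unplanned healthcare utilization".
- **Schedule of Assessments.** "Adverse Drug / Withdrawal Events" has its own row, marked at baseline, SNF discharge, 7 days and 90 days. Unplanned utilization is a different row.
- **Protection Against Risks.** Daily nursing observation in the SNF is presented as a strength of the trial, and "Medications can be restarted or increased at any time should adverse pharmacokinetic/pharmacodynamics effects or a physiologic drug withdrawal effect be detected".

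**The concern.** The intervention stops or reduces drugs, so withdrawal effects and return of symptoms are the harms most specific to it. The plan places its safeguard in the SNF: staff receive the list of deprescribed drugs, watch the patient, and a drug can be restarted. When that safeguard works early, there is no emergency visit, no admission and no death, and so, under the definition, no event. The better on-site monitoring works, the fewer withdrawal events are recorded.

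Two things are at stake. First, the DSMB is asked to weigh risk against benefit and would do so without the milder withdrawal signal. Second, a reader of the final report could take a low ADWE count as evidence that withdrawal effects were rare, when the count covers only those that led to hospital-level care or death. Capture may also differ between arms, because the handover of deprescribed drugs and monitoring needs prompts SNF staff to detect and manage effects on site.

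**Working it through.** The plan states no expected ADWE or restart rate, so there is no figure to reproduce. The check is a trace through the text, followed by an illustration of scale.

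**1. Can a withdrawal effect handled on site enter the safety data?**

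| Section | Trigger or question | On-site restart captured as a safety event? |
|---|---|---|
| Safety Monitoring and Assessments | Utilization or unexpected death | No |
| Notification of Unplanned Healthcare Utilizations and Deaths | ICU transfer, emergency visit, hospitalization, death; at follow-up, patients are asked about emergency and inpatient care | No |
| Safety Outcomes; Review of Unplanned Healthcare Utilizations and Deaths | Adjudication starts from a utilization or unexpected death | No |
| Skilled Nursing Facility (SNF) | Weekly contact: discharge date and utilization | No |
| Data Safety Monitoring Board | Listings of deaths, serious and non-serious adverse events | No: the listings use the same definition of an adverse event |
| Schedule of Assessments | Separate row for adverse drug and withdrawal events | Suggested, but no collection method is described beyond utilization review |

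**2. Where would it leave a trace?** A drug that is back in use at a time point appears in the medication lists at SNF discharge, 7 days and 90 days (Primary Outcomes – Medications; 7- and 90-Day Follow-Up). No step labels it a restart, records why it happened, or sends it to the DSMB.

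**3. Scale, as an illustration only.** Inputs: 260 patients randomized 1:1 (Sample Size and Randomization), so 260 / 2 = 130 per arm. Pilot means of pre-hospital drugs deprescribed were 6.1 with the intervention and 4 in control (Preliminary Data). The restart rate of 5-10% is an assumption.

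- Drugs deprescribed: 130 × 6.1 = 793 and 130 × 4 = 520.
- Restarts at 5%: 0.05 × 793 ≈ 40 and 0.05 × 520 = 26.
- Restarts at 10%: 0.10 × 793 ≈ 79 and 0.10 × 520 = 52.

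The pilot totals of 12.6 and 6.5 also include drugs that were not taken before admission, for which a restart after discharge is less plausible. They would give 130 × 12.6 = 1,638 and 130 × 6.5 = 845 drugs, or 82-164 and 42-85 restarts. I do not rely on them.

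**4. Why raw counts would mislead.** Step 3 uses the same risk per drug in both arms, yet the counts differ by a factor of 793 / 520 = 1.5, only because more drugs were stopped. The proportion of deprescribed drugs restarted is equal by construction. The proportion of patients with at least one restart is not free of this effect. Taking every patient at the pilot mean, with independent risks, it is 1 − (1 − r)^k:

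- r = 5%: 1 − 0.95^6.1 = 26.9% versus 1 − 0.95^4 = 18.5%.
- r = 10%: 1 − 0.90^6.1 = 47.4% versus 1 − 0.90^4 = 34.4%.

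The two measures therefore answer different questions. The patient-level measure keeps the randomized comparison and shows total burden. The per-drug measure shows risk per drug stopped, but its denominator arises after randomization.

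**The case against.** The best defence has five parts.

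- **The information is not lost.** A reader might infer that on-site withdrawal effects are recorded nowhere. That goes too far. Restarts still in force show in the medication lists, dose increases of anticholinergic and sedative drugs show in the Drug Burden Index, and pain, depression and falls are assessed in both arms at 7 and 90 days. This stands. But these are outcome data with no link to a withdrawn drug, and the summary of actual medication changes under Hypotheses 1a-1b is planned for the intervention group only.
- **Restarts are permitted, not forecast.** A reader might take Protection Against Risks as predicting restarts. Its wording is conditional, so it supports no rate. This stands.
- **Safety is not a tested hypothesis.** Hypotheses 1a to 2b do not concern withdrawal events, and the analysis sections plan no comparison of ADWEs. The overarching hypothesis speaks of reducing drugs safely, but a formal conclusion of no excess is not announced. This stands and limits the consequence to interpretation and DSMB oversight.
- **Wider capture may have been intended.** The separate schedule row and the listing of non-serious adverse events point that way, and the case report forms are not in the documents. This is a reason to reconcile the text, because no described procedure delivers it. Under the current definition, a non-serious event would be, for example, an emergency visit without admission.
- **The numbers are soft.** The pilot had 20 non-Veterans per group, no attrition is applied, and the restart rate is assumed. All of this is correct. The gap in the definition does not depend on it.

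**Conclusion.** The concern holds in a limited form. By the plan's own rules, a withdrawal effect that is detected and managed without an ICU transfer, emergency visit, hospitalization or unexpected death is not classified as an adverse event or ADWE and is not reported to the DSMB. This rests on the text alone. It sits uneasily with the schedule, which lists such events apart from utilization, and with the reliance on SNF monitoring to detect them.

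The number of events outside the definition cannot be derived from the documents. The restart figures show only that it need not be trivial, and they count all restarts, some of which may not be harms or may also have led to utilization. A reader might infer that nearly all withdrawal harms are missed, or that the trial conceals an excess of harm. The documents support neither: they give no share of withdrawal effects that lead to utilization and no harm rate by arm.

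The point does not affect the primary medication outcomes. It is an inexpensive improvement to the safety assessment.

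**What to change.** 1. **Reconcile the text.** Make Schedule of Assessments, Safety Outcomes, Safety Monitoring and Assessments, Review of Unplanned Healthcare Utilizations and Deaths, and Protection Against Risks agree on what an ADWE is and how it is collected. If the definition tied to utilization stays, say so wherever ADWE counts are reported.
2. **Add a secondary safety measure from existing data.** Count deprescribed drugs restarted or increased again by SNF discharge, 7 days and 90 days, identified in the same way in both arms from the enrollment, hospital discharge and later lists. State how drugs scheduled to stop or taper after discharge are handled, and which time points apply to Veterans who went home without an SNF stay.
3. **Report it to the DSMB by arm** as a proportion of drugs deprescribed and as patients with at least one restart, not as raw counts.
4. **Where follow-up is still open,** add one reason code to the medication review at the 7- and 90-day calls. The stated timeline ends follow-up in March 2023. After that only the list-derived measure is realistic, because reasons not asked at the time cannot be recovered reliably.
5. **Keep blinded adjudication** for utilization events.

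The cost is one derived variable, one reason code and one DSMB table, with a little extra time on calls already made. The downsides are that these events are unadjudicated, that reasons are recorded by study clinicians who are not blinded, that restarts reversed between time points are missed, and that a restart without a reason is not necessarily a harm. No change to clinical management is implied.
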